13.1 Primary Safety Analysis

All participants who have been exposed to study treatment will be included in the **safety** analyses.

For the primary safety analysis, \geq Grade 3 AEs attributed to study treatment and confirmed CD4+ declines (see **protocol** section 9.2.1.1) will be summarized (including listing of events).

In addition, all reported AEs \geq Grade 3 (regardless of treatment relatedness) will be summarized (**listing**) and a table showing the maximum (for each participant) grade event attributed to study treatment.

Listings identifying the following:

Event description, grade, **lab value and units, treatment week of event**, and relationship to study treatment (as judged by the core team) that occurs any time from the initial dose of sirolimus to the end of study follow-up.

Similar listings restricted to lipids, glucose and creatinine, respectively.

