6.3.4 Clinical Assessments

Complete Physical Exam

A complete physical examination to include at a minimum an examination of the skin, head, mouth, and neck; auscultation of the chest; cardiac exam; abdominal exam; examination of the lower extremities for edema. The complete physical exam will also include signs and symptoms, diagnoses and vital signs (temperature, pulse, respiration rate, pulse oximetry and blood pressure).

Targeted Physical Exam

A targeted physical examination to include vital signs (temperature, pulse, respiration rate, pulse oximetry and blood pressure); examination of the skin, head, mouth, and neck; auscultation of the chest; cardiac exam; and is to be driven by any previously identified or new signs or symptoms and diagnoses that the **participant** has experienced since the last visit. Assessment of new pulmonary symptoms, including cough, shortness of breath and dyspnea on exertion will be included in the targeted exam.

Height

Height will be recorded at entry.

Weight

Weight will be recorded at entry and **all subsequent study visits**.

Signs and Symptoms

At entry, all grades of signs and symptoms that occurred within 30 days before entry must be recorded; post-entry, all grades of Grade ≥ 2 must be recorded. Record **on the CRF and key within 48 hours** all signs and symptoms regardless of grade that led to a change in study treatment or a change in ART. All Grade 3 or higher sign/symptom, any sign/symptom regardless of grade that led to a change in study treatment, or that met ICH, EAE or SAE guidelines, are defined by the protocol as reportable events that will require more detailed event reporting and keying within 48 hours.

Diagnoses

After entry, record all diagnoses identified by the ACTG criteria for clinical events and other diseases. Diagnoses must be recorded and keyed within 48 hours of the evaluation.

Concomitant Medications

After entry, record new or discontinued concomitant prescription and nonprescription drugs since the last visit.

ART Medication Modifications

At entry, record all ongoing ART. After entry, record all modifications in ART, including initial doses and/or missed doses (defined as more than 2 consecutive doses), inadvertent and deliberate interruption, and discontinuation.

Study Treatment Modifications

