9.6.1 Primary Analyses

For the primary safety analysis, \geq Grade 3 AEs attributed to study treatment and confirmed CD4+ declines (see section 9.2.1.1) will be summarized. In addition, all other reported AEs \leq Grade 2 attributed to study treatment as well as all reported events \geq Grade 2 (regardless of treatment relatedness) will be summarized. All **participants** who have been exposed to study treatment will be included in the analysis.

For the primary immunologic (see section 9.2.1.2) and virologic (see section 9.2.1.3) efficacy outcomes, post-treatment changes will be evaluated comparing measurements pre-treatment (averaged) to the measurement 20 weeks after starting study treatment, testing the null hypothesis of no difference pre-treatment versus post-treatment using a paired t-test. Log-transformations may be applied for the virologic outcomes. To address anticipated left-censoring of SCA measurements, a value one half the lower assay limit will be imputed. If feasible with the modest sample size, censored-data longitudinal data methods that statistically address the

issue of left-censoring (SCA measurements below assay limits) will also be used to evaluate and estimate treatment effects [59]. Mean and quartile plots will summarize the immunologic and virologic measurements at each visit. Because the aim of this pilot study is to investigate the biologic effects of sirolimus, the analyses will be as-treated, limited to **participants** who have data at baseline and week 32 (20 weeks on sirolimus) and who remained on study treatment and ART (and without virologic failure) through week 32. A supplemental analysis will be based on changes from baseline to the last available time point for a **participant** while on study treatment and ART (and without virologic failure).

If there is evidence that there is a significant difference between the week 0 and week 12 levels of the primary immunologic and virologic efficacy measurements, based on paired t-tests between these two time points, then the primary analysis will instead be based on a comparison of slopes pre- versus post-treatment (see 9.6.2). Both sets of results, from the paired t-test analyses and the comparison of slopes analyses, will be reported in the presentation of the study findings.

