12.1 Signs/Symptoms, Abnormal Laboratory Test Values and Diagnoses

List: showing **all grades of safety events** for each study participant. The list will include the following:

- public ID
- core team assigned code (regarding the relatedness to study treatment)
- **treatment week of event**
- event description
- value and units (for laboratory results)
- grade

NOTE: This information corresponds to the ToxSum report prepared by the DMC

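### SAP 13.1 sets the adverse event summary that ignores relatedness at Grade 3 or higher, where protocol 9.6.1 promises Grade 2 or higher, so the only planned table that can show Grade 2 is limited to attributed events

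*SAP*

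**What the plan says.** Protocol 9.6.1 names three safety summaries. The first, the primary one, covers attributed events of Grade 3 or higher and confirmed CD4+ declines. The second covers attributed events at or below Grade 2. The third covers all reported events at or above "Grade 2 (regardless of treatment relatedness) will be summarized". All participants exposed to sirolimus are included.

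SAP 13.1 keeps the first summary. Of all reported events of Grade 3 or higher it then says "regardless of treatment relatedness) will be summarized (listing) and a table showing the maximum (for each participant) grade event attributed to study treatment". The summary that ignores relatedness thus starts at Grade 3, and the maximum-grade table, for which no lowest grade is stated, takes the place of the attributed lower-grade summary. It adds listings for lipids, glucose and creatinine, also without a stated grade floor.

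SAP 12.1 separately plans a list of "all grades of safety events for each study participant". The core team's relatedness code is one of its columns and does not filter the entries.

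**The concern.** The trial has no control arm and no blinding, and the core team decides relatedness. The adverse event part of the primary safety outcome already rests on that judgement. A count that ignores attribution is the natural check on it, and the protocol promised one from Grade 2 upward.

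Grade 2 is not a trivial level in this study. Hypothesis 1.1.1 is that sirolimus will be safe and tolerated, and protocol 7.2.2 has sirolimus held for Grade 2 dyspnea. SAP 5.3 reports that 13 of 29 participants (45%) had at least 6 but less than 20 weeks of sirolimus. It gives no reasons, so this is not evidence of toxicity, but it means that readers will look closely at tolerability. If Grade 2 is tabulated only for attributed events, they cannot see from the tables how far the picture depends on the team's attribution.

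**Working it through.** The plan gives no figure on this point. Its one numerical safety statement, in protocol 9.4, concerns the chance of seeing at least one related event with a true rate of 8% among 30 participants: 1 − 0.92^30 = 0.918. That reproduces the stated value of more than 90%, and nothing here changes it. The rest is a comparison of text.

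**Step 1. The planned outputs side by side.**

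| Place | Grades | Restricted to attributed events? | Form |
|---|---|---|---|
| Protocol 9.6.1 | 3 or higher, plus confirmed CD4+ declines | Yes (events) | Summary |
| Protocol 9.6.1 | 2 or lower | Yes | Summary |
| Protocol 9.6.1 | 2 or higher | No | Summary |
| SAP 13.1 | 3 or higher, plus confirmed CD4+ declines | Yes (events) | Summary with listing |
| SAP 13.1 | 3 or higher | No | Listing |
| SAP 13.1 | Participant's maximum, no floor stated | Yes | Table |
| SAP 13.1 | Lipids, glucose, creatinine, no floor stated | Not stated | Listings |
| SAP 12.1 | All | No | Listing |

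The third row has no counterpart in SAP 13.1 at Grade 2.

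**Step 2. Where a Grade 2 event can appear under the SAP.**

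- *Judged related:* in the 12.1 listing, and in the maximum-grade table if the participant has no attributed event of higher grade. A participant with an attributed Grade 3 event enters that table at Grade 3, so the Grade 2 event is not visible there.
- *Judged unrelated:* in the 12.1 listing, and perhaps in a 13.1 listing if it is a lipid, glucose or creatinine value. It appears in no table.

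**Step 3. Whether the data support a Grade 2 count.** Protocol 6.3.4 requires post-entry signs and symptoms to be recorded from Grade 2. Protocol 6.3.5 requires lipids, glucose, hematology, liver tests, creatinine clearance and creatinine at every grade, and other laboratory values from Grade 3 (lower if they changed study treatment or ART). A count of reported events from Grade 2 is therefore complete by design for symptoms and the named tests. For the remaining tests it effectively starts at Grade 3.

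**Step 4. An illustration from the protocol.** Section 2.2.4 describes a study of 7 participants in which Grade 3 events occurred in two and another participant had a Grade 2 pneumonia treated with oral antibiotics. Taking that participant as distinct from the two, as the text suggests, the number with an event regardless of relatedness is 2 of 7 with a Grade 3 floor and at least 2 + 1 = 3 of 7 with a Grade 2 floor. Had the pneumonia been judged unrelated, it would enter no table planned in SAP 13.1. This shows the mechanism; it does not predict this trial's result.

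**The case against.** The best defence is that nothing is withheld. SAP 12.1 lists every grade without regard to attribution. The protocol says only that these events will be summarised and promises no counts, and SAP 13.1 itself treats a listing as a summary. With about 30 participants, a reader could count from the list. There are other safeguards too. Possibly related events count as related, the core team takes account of the site investigator's opinion, the monitoring committee sees each relatedness decision, and discontinuations are reported with reasons. A Grade 2 dyspnea that leads to a hold is a reportable event whatever its attribution.

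Most of this stands, and it rules out four stronger readings:

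- A reader might infer that every Grade 2 summary now depends on attribution. The 12.1 listing does not.
- A reader might infer that the maximum-grade table starts at Grade 1 and shows participants with only mild symptoms as event-free. SAP 13.1 states no lowest grade and no row for participants without events.
- A reader might infer an unlogged change because the SAP's update list is silent. That list covers changes between SAP versions, not departures from the protocol. The Grade 3 floor is also not in the bold type that marks major changes since SAP version 1.0, so it may date from that version.
- A reader might blame SAP 13.1 for the uneven recording of low grades. Those rules come from protocol 6.3.4 and 6.3.5, and the protocol's own summary of attributed events at or below Grade 2 carries the same unevenness.

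What does not stand is that the listing replaces the summary. SAP 12.1 plans no counts. It covers each study participant and states no start point, so it may include events from the 12-week lead-in, whereas the listings in 13.1 run from the first dose. SAP 4.3 keeps participant identifier numbers out of final listings while 12.1 includes a public ID, so it is unclear whether an outside reader could reduce lines to participants. Even on the view that a listing is a summary, the grade floors in protocol 9.6.1 and SAP 13.1 differ and no reason is given.

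**Conclusion.** The point holds as a discrepancy between protocol and SAP in a supporting safety analysis. The floor for the summary that ignores relatedness is one grade higher in SAP 13.1 than in protocol 9.6.1, without explanation. The only planned table that can show Grade 2 is restricted to attributed events. Events remain visible individually; the missing item is the count.

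The primary safety outcome, the efficacy analyses and the sample size statement are untouched. How many Grade 2 events would be affected cannot be stated, because the documents give no adverse event data for this trial. The conclusion assumes that SAP 13.1 is meant to implement protocol 9.6.1, and that no table outside the SAP supplies the count.

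**What to change.** Change SAP 13.1 to match protocol 9.6.1. For exposed participants, from first sirolimus dose to end of follow-up, tabulate the number with any reported event of Grade 2 or higher, by event and maximum grade, regardless of relatedness. Place it beside the table of attributed events so that the two can be compared directly. If the higher floor was intended, give the reason in the SAP.

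If the attributed-event table shows Grade 1, add a footnote: post-entry Grade 1 symptoms had to be recorded only when they led to a change in study treatment or ART, or met the serious or expedited reporting criteria (protocol 6.3.4), so that row is incomplete for symptoms.

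The cost is a sentence or two of SAP text and about one extra table from data already in the safety listing. No new data are needed.

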13.2 Primary Efficacy Analyses

Because the aim of this pilot study is to investigate the biologic effects of sirolimus, the primary efficacy analysis population is defined as participants who completed the full 20 weeks of sirolimus treatment, and who remained on sirolimus and ART without virologic failure. For each primary efficacy outcome, analysis will be limited to participants who have data both at baseline and after 20 weeks of sirolimus. Based on the specimens mobilized for testing, 16 participants are anticipated to meet these criteria and be included in the primary efficacy analysis.

Tables summarizing completeness (N), mean, standard deviation, median, 25th and 75th percentiles and min/max of HIV-1 Gag-specific CD8+ T-cells by intracellular staining for IFN-gamma, CD4+ T-cell associated HIV-1 RNA, and plasma HIV-1 RNA by SCA at baseline and at **treatment week 20**.

For the primary immunologic and virologic efficacy outcomes, post-treatment changes will be evaluated comparing measurements pre-treatment (averaged) to the measurement 20 weeks after starting study treatment, testing the null hypothesis of no difference pre-treatment versus post-treatment using a paired t-test.

Log10-transformations will be applied for the virologic outcomes.

Cell-associated HIV-1 RNA (CA-RNA) was measured in terms of copies/ 10^6 PBMCs. These results were normalized to copies/ 10^6 CD4+ T-cells by dividing by (CD4% / 100).

To address anticipated left-censoring of SCA and CA-RNA measurements, a value one half the lower assay limit will be imputed and analyzed for results below assay limit. If feasible with the modest sample size, censored-data longitudinal data methods that statistically address the issue of left-censoring (SCA measurements below assay limits) will also be used to evaluate and estimate treatment effects [Vaida and Liu 2009]. Plots will summarize the

immunologic and virologic measurements at each visit (means over time, participant-specific curves).

If there is evidence that there is a significant **effect of sirolimus on a primary immunologic or virologic efficacy outcome and also a significant** difference between the week 0 and week 12 (**treatment weeks -12 and 0**) levels of the measurements, based on paired t-tests between these two time points, then **additional analyses and summaries will be performed. In particular**, the primary analysis will be supplemented with an analysis based on a comparison of slopes pre- versus post-treatment. Both sets of results, from the paired t-test analyses and the comparison of slopes analyses, will be reported.

For the primary efficacy analysis population, a summary/listing of gaps or holds in sirolimus or ART use from entry through treatment week 32*.

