9.4 Sample Size and Accrual

Regarding the assessment of safety/toxicity (see section 9.2.1.1), the sample size of 30 sirolimus-treated **participants** will provide >90% probability of observing a sirolimus-related adverse event that would occur in 8% or more of treated **participants**.

The primary efficacy analyses will evaluate paired baseline and post-sirolimus therapy immunologic and virologic measurements to detect changes; these measures are assumed stable on long-term suppressive ART (see section 2.2.6). Allowing 17% sample size adjustment for lost to follow-up and treatment discontinuation for the planned as-treated analyses (i.e., n=25 **participants** assumed evaluable), the study will have 80% power to detect a 0.59 standard deviation (SD) effect size based on a two-sided, alpha=0.05, 1-arm t-test. This effect size translates (under assumed normality) into a probability of 0.72 that a **participant** receiving sirolimus will have an observed increase in HIV-specific CD8 immunity (see section 9.2.1.2). Similarly, power would be 80% to detect a corresponding decrease in cell-associated RNA (see section 9.2.1.3). The null hypothesis is that the probability is 0.5 (equally likely to observe increase or decrease). For residual viremia (SCA, see section 9.2.1.3), effect size is slightly larger due to anticipated left-censoring below assay limits. From numerical simulation based on a 1-arm t-test (imputing half the lower limit for SCA results below assay limits), power is estimated to be 80% to detect an underlying effect size of 0.67 SD; this 80% power corresponds to assuming that the probability is 0.5 (50%) for a baseline (pre-entry, entry) SCA to be below assay limit compared to 0.75 (75%) after treatment. The assumption that 50% of SCA results will be below assay limits at baseline is supported by findings from ACTG A5276s in which 56% of 668 SCA measurements after 192 and 208 weeks of suppressive ART on 334 **participants** were below assay limits (<1 copy/mL). Analyses will also jointly evaluate efficacy measurements at the multiple post-treatment time points (e.g., the change from baseline to the average of the weeks 16, 24, and 32 measurements [4, 12, 20 weeks on sirolimus]), which could increase statistical power.

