9.6.2 Secondary Analyses

Additional analyses of safety will summarize the magnitude of CD4+ cell changes baseline to post-treatment time points (mean, quartiles). Analyses will also summarize the number of **participants** who exhibit on two consecutive measurements HIV RNA >200 copies/mL on conventional assay. Tolerability will be assessed by the number of **participants** who prematurely discontinue study treatment and the reasons for discontinuation.

Analyses of secondary virologic and immunologic outcomes will parallel the primary analyses outlined in section 9.6.1. Graphical approaches will summarize the virologic and immunologic measurements over time. Supplemental analyses will compare the change in the slope-over-time pre-treatment (pre-entry to start of treatment) versus post-treatment (start of treatment through week 20 while on treatment) and also may examine the change from baseline to the average of the week 16, 24 and 32 (4, 12, 20 weeks on sirolimus) measurements. Soluble markers (e.g., IL-6 levels) will be log-transformed.

Analyses will also summarize changes in immunologic and virologic measures after discontinuation of study treatment.

Associations between changes in the various immunologic and virologic measurements will be evaluated using scatterplots and correlations coefficients.

The relationship between anal HPV, particularly HPV 16, and immunological measurements of activation and virological measurements of HIV reservoir size will be correlated.

The effect of study treatment on anal dysplasia will be described by evaluating the change in anal Pap tests after study therapy. Pap tests will be categorized as

normal or abnormal according to standard clinical criteria.

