3 STUDY SCHEMA, HYPOTHESIS AND OBJECTIVES

Note: The following material is extracted from the study protocol Version **2.0**, **L.O.A. #1** and **C.M. #1** and **2**.

STUDY SCHEMA

DESIGN

A5337 is a phase I/II, open label, single arm, pilot study to evaluate the safety of sirolimus and its efficacy with respect to its effects on HIV-1 reservoir size and immune function. This study will assess the effects of sirolimus on HIV-1-specific CD8+ T-cell function, HIV transcription, and residual viral production. Measurement of additional inflammatory markers, immunological studies, and reservoir size will be performed on stored specimens if the initial findings appear promising.

DURATION

44 weeks (12-week pre-sirolimus treatment lead-in period, followed by 20 weeks of sirolimus treatment and an additional 12 weeks off sirolimus treatment).

SAMPLE SIZE

30 participants

Target enrollment was 30 participants in order to achieve n = 25 evaluable participants for the as-treated primary efficacy analysis population.

POPULATION

HIV-infected men and women ≥ 18 years of age, maintained on suppressive antiretroviral therapy (ART) for ≥ 24 months with CD4+ cell count ≥ 350 cells/mm³. **Participants** may not be on a PI-based or cobicistat-based regimen 3 months prior to and at any time after study entry and must remain on ART during sirolimus study treatment.

STRATIFICATION

By class of antiretroviral (ARV) regimen

REGIMEN

For **participants** on a non-protease inhibitor (PI), non-nucleoside reverse transcriptase inhibitor (NNRTI) regimen, and for those on a non-PI, rilpivirine (RPV) based regimen:

Sirolimus 0.025 mg/kg/day initial dose for 20 weeks

For **participants** who are on an NNRTI regimen with the exception of RPV:

Sirolimus 0.05 mg/kg/day initial dose for 20 weeks.

Dosing will be adjusted based on trough sirolimus concentrations to achieve target concentrations between 5 and 10 ng/mL.

HYPOTHESES

Sirolimus will be safe and tolerated in **participants** on non-protease inhibitor (PI) suppressive antiretroviral therapy (ART).

Sirolimus will improve HIV-specific cellular immunity and reduce T-cell activation, which in turn will cause decreases in viral transcription/cell-associated RNA levels and levels of low-level residual viremia.

Sirolimus will cause down-regulation of programmed cell death protein (PD-1) and suppression of homeostatic proliferation of the latent reservoir, leading to reductions in cell-associated HIV-1 DNA levels.

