5.3 Visit Schedule and Definition of Week for Analysis Purposes

The visit schedule for key study outcomes is shown in Table 1.

The protocol requires evaluations to be scheduled at the **treatment week 0** visit, ± 1 day at the **treatment week 1, 2 and 4** visits, ± 1 week at the **treatment week 8, 12 and 20** visits, and ± 2 weeks at the **treatment week 32*** visit. The analysis window for post-entry visits will be calculated based on the number of **weeks** since the initial dose of sirolimus and broader windows will be used (as compared to the protocol specified window) in order to minimize the impact of deviations from the desired schedule. If there are multiple evaluations within the window for a given visit, then the evaluation closest to the scheduled study week will be used (and the later measurement will be used if there are two measurements which are equally distant from the scheduled week). Table 1 **below** details the **analysis windows for clinical data**.

For the primary and secondary outcome measures, and the exploratory soluble marker outcome, a database review was conducted by the study chair to identify the time points to be tested based on the availability of samples and the duration of sirolimus use. This resulted in a total of 159 time points for 29 study participants.

- For 16 participants with the full 20 weeks of sirolimus use who will constitute the primary efficacy population: treatment weeks -12, 0, 4, 12, 20 and 32*
- For the 13 participants with at least 6 but less than 20 weeks of sirolimus use: treatment weeks -12, 0, 4, 12 and 20*

Note: One participant went off study early and only has weeks -12, 0 and 4.

Note: Treatment weeks 32* and 20* refer to time points after sirolimus discontinuation. Data from these time points will be used to assess durability of treatment effects and will not be included in the as-treated analysis of efficacy.

Table 1: Study Visit Schedule and Analysis Windows

Evaluation	Screening	Entry	Sirolimus Initiation	Post-Entry Evaluations						
	Treatment Week	-12	0	1	2	4	8	12	20	32
Analysis Window (Weeks Post-Sirolimus Initiation)		0	(0 – 1]	(1 – 3]	(3 – 6]	(6 – 10]	(10 – 16]	(16 – 26]	(26 – 37]	
Clinical Assessment	X	X	X	X	X	X	X	X	X	X
Hematology	X	X	X	X	X	X	X	X	X	X
Liver Function Tests	X	X	X	X	X	X	X	X	X	X
Blood Chemistry	X	X	X	X	X	X	X	X	X	X
Calculated Creatinine Clearance	X	X	X	X	X	X	X	X	X	X
Urinalysis	X		X			X	X	X		
CD4+/CD8+	X	X	X		X	X	X	X	X	X
Plasma HIV-1 RNA	X	X	X			X	X	X	X	X

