14 SECONDARY OUTCOME MEASURES

ANALYSES:

Additional analyses of safety will summarize the magnitude of CD4+ T-cell changes baseline to post-treatment time points (means over time, participant-specific curves). Analyses will also summarize the number of **participants** who exhibit on two consecutive measurements HIV RNA >200 copies/mL on conventional assay. Tolerability will be assessed by the number of **participants** who prematurely discontinue study treatment and the reasons for discontinuation. **The analysis population for these CD4, HIV-RNA, and tolerability assessments will be the safety population.**

Analyses of secondary virologic and immunologic outcomes will parallel the primary analysis. **The secondary efficacy analysis population is defined as participants who completed at least 6 weeks of sirolimus.** Paired t-tests will compare measurements pre-treatment (averaged) to the measurement at treatment week 20 for the primary efficacy population and treatment week 4 for the secondary efficacy population. Graphical approaches will summarize the virologic and immunologic measurements over time, **through treatment week 32 for the primary efficacy population and, separately, through treatment week 4 for the secondary efficacy population.** Soluble markers (eg, IL-6 levels) will be log10-transformed.

Analyses will also summarize changes in immunologic and virologic measures after discontinuation of study treatment. **Paired t-tests will compare the measurements at treatment week 20 to treatment week 32* for the primary efficacy analysis population.**

For the primary analysis population, trough sirolimus levels (during the 20 weeks of treatment) will be summarized by descriptive statistics on the participant-specific average of all available sirolimus levels (minimum, 10th, 25th, median, 75th, 90th, maximum). In addition, the number of trough levels per participant will be summarized. To provide information regarding pharmacodynamics, scatterplots and correlations

will assess the relationship between average trough level and change from baseline to week 20 outcomes. These correlations will be restricted to outcomes with evidence of change following sirolimus treatment.

Associations between changes in the various immunologic and virologic measurements will be evaluated using scatterplots and correlations coefficients.

OUTCOMES:

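### With the 16 participants the SAP expects, power for the protocol's 0.59 SD effect is about 60%, not 80%; the SAP states no revised figure and omits the protocol's last-on-treatment supplemental analysis.

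*SAP*

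**What the plan says.** Protocol 9.4 allows 17% for loss to follow-up and treatment discontinuation, which leaves 25 of 30 evaluable, and says "the study will have 80% power to detect a 0.59 standard deviation (SD) effect size based on a two-sided, alpha=0.05, 1-arm t-test". It translates 0.59 SD into a probability of 0.72 that a treated participant shows an increase. For the single-copy assay (SCA) it gives 80% power at 0.67 SD, from a simulation. SAP section 3 keeps the same rationale: "Target enrollment was 30 participants in order to achieve n = 25 evaluable participants for the as-treated primary efficacy analysis population".

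SAP 13.2 then gives the number now expected: "Based on the specimens mobilized for testing, 16 participants are anticipated to meet these criteria and be included in the primary efficacy analysis". It also requires baseline and week-20 data for each outcome. SAP 5.3 shows where the others went. Of 29 participants with samples selected for testing, 16 had the full 20 weeks of sirolimus. The samples for the rest are listed under "For the 13 participants with at least 6 but less than 20 weeks of sirolimus use": treatment weeks -12, 0, 4 and 12, and an off-drug week 20. A note adds: "One participant went off study early and only has weeks -12, 0 and 4".

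On supporting analyses, protocol 9.6.1 makes the as-treated completer test primary and adds: "A supplemental analysis will be based on changes from baseline to the last available time point", restricted to time on study treatment and ART without virologic failure. Protocol 9.6.2 says that supplemental analyses "also may examine the change from baseline to the average of the week 16, 24 and 32" (treatment weeks 4, 12 and 20). SAP 14 says that paired tests for the secondary virologic and immunologic outcomes compare baseline "to the measurement at treatment week 20 for the primary efficacy population and treatment week 4 for the secondary efficacy population", where the secondary efficacy population has at least 6 weeks of sirolimus.

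**The concern.** The only power figure in the two documents belongs to a sample of 25 that the trial no longer expects. A non-significant primary result could therefore be taken as evidence against a 0.59 SD effect when the test had only a moderate chance of finding one. SAP 13.2 lists means, SDs and quantiles at baseline and week 20, but names no confidence interval for the change that would show the imprecision directly.

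The heavier loss also makes the protocol's last-on-treatment analysis more important than it was at design. It is the one clear commitment to bring early stoppers' on-treatment data into the three primary efficacy outcomes. No SAP section contains it, and the SAP's version history does not record its removal.

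**Working it through.** **Inputs.** Effect 0.59 SD of the paired change, two-sided alpha 0.05, one-sample t-test, n = 25 (protocol 9.4); n = 16, with 13 early stoppers among 29 tested (SAP 5.3 and 13.2).

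**Method.** Exact power is P(|T| > t(0.975, n-1)), where T is noncentral t with n-1 degrees of freedom and noncentrality 0.59 × √n.

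**Protocol figure.** At n = 25 the noncentrality is 0.59 × 5 = 2.95 and power is 0.808, so the stated 80% reproduces. So do the loss allowance (30 × 0.83 = 24.9) and the probability (Φ(0.59) = 0.722).

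**Same calculation at the SAP's number.** At n = 16 the noncentrality is 0.59 × 4 = 2.36.

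| | n = 25 | n = 16 |
|---|---|---|
| Power for 0.59 SD | 0.808 | 0.598 |
| Effect with 80% power | 0.584 SD | 0.749 SD |
| 95% CI half-width, t(0.975, n-1)/√n | 0.413 SD | 0.533 SD |

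The interval is wider by 0.533/0.413 = 1.29. The 0.749 SD effect corresponds to Φ(0.749) = 0.773, against the protocol's 0.72. Because each outcome needs both time points, 16 is a ceiling: power is 0.566 at n = 15 and 0.533 at n = 14.

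**Attrition.** Planned evaluable 25/30 = 83%; expected 16/30 = 53%. Among those tested, 13/29 = 45% are outside the primary set.

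**SCA.** The protocol's simulation depends on a within-person correlation that the documents do not give. For a shift from 50% to 75% below the limit, with half-limit imputation and the mean of two baseline values, assumed correlations of 0.2, 0.4 and 0.6 give power of 0.71, 0.79 and 0.89 at n = 25, and 0.51, 0.59 and 0.70 at n = 16. Wider assumptions (correlation 0 to 0.7, single or averaged baseline) give 0.479 to 0.944 at n = 25 and 0.315 to 0.780 at n = 16. The level is uncertain, but power falls in every scenario.

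**Week-12 samples from early stoppers.** SAP 5.3 counts 159 time points. This equals 16 × 6 + 12 × 5 + 1 × 3 = 159, so at most 12 of the 13 early stoppers have a week-12 sample. How many were still on sirolimus then is not stated.

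**Power of the last-on-treatment analysis (n = 29).** This depends on how fast the effect builds, which is assumed here. The SD of the change is set to 1, and 0 to 12 of the 13 early stoppers contribute week 12; the others contribute week 4.

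| Share of the 0.59 SD effect at weeks 4/12/20 | Average effect in the 29 (0 to 12 at week 12) | Power |
|---|---|---|
| 100/100/100% | 0.59 SD | 0.87 |
| 50/80/100% | 0.59 × 22.5/29 = 0.46 to 0.59 × 26.1/29 = 0.53 SD | 0.66 to 0.79 |
| 25/50/100% | 0.59 × 19.25/29 = 0.39 to 0.59 × 22.25/29 = 0.45 SD | 0.51 to 0.65 |

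The first row is exact; the other two are from simulation. The analysis can have more or less power than the completers' 0.60, so it supplements the completer test and cannot be counted on to recover the lost power.

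**The case against.** The strongest reply is that no document is in error on power. The 80% is tied to 25 participants and is correct there. The SAP does not repeat it, gives its target in the past tense, and discloses the 16 openly. The sample can no longer change, so a revised power figure alters no decision, and a confidence interval would serve the reader better. This largely stands, and it is why the remedy gives the detectable effect and confidence intervals and not a power figure alone. It does not remove the gap, because the SAP supplies none of these.

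On the supplemental analysis, the SAP's week-4 comparison uses participants with at least 6 weeks of sirolimus, which on the SAP 5.3 counts means all 29, at a time when all had been on drug. That is a sensible common time point and avoids mixing exposure durations. But it is worded for secondary outcomes, and early stoppers' week-12 values enter no stated paired test. SAP 5.3 marks only the weeks after discontinuation with an asterisk, and week 12 is unmarked. That suggests it was regarded as on-treatment, although a minimum of 6 weeks also allows a stop before week 12.

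It can also be said that the protocol offers other routes. Section 9.4 says efficacy measurements at several time points will be analysed jointly, and 9.6.2 plans a slope comparison while on treatment. Neither says that early stoppers enter the primary outcomes, and 9.6.1 makes slopes conditional for those outcomes. The left-censoring method in SAP 13.2 is subject to feasibility, is aimed at SCA, and is not said to extend beyond the completers.

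**Conclusion.** The concern holds in both parts. For Gag-specific CD8+ frequency and cell-associated RNA, power for the protocol's effect is about 0.60 with 16 participants, and 80% power requires about 0.75 SD. These figures use the protocol's own test and need no further assumption. The cause is heavier attrition than planned, not faulty arithmetic. SCA power also falls, by an amount that cannot be fixed from the documents. The last-on-treatment analysis is a protocol commitment missing from the SAP without explanation, and the week-4 test does not replace it.

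The primary test remains valid. What needs correcting is how a null result would be read, and the missing analysis. This should be fixed.

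**What to change.** 1. In SAP sections 3 and 13.2, state that with 16 participants in the primary efficacy population, power for a 0.59 SD change is about 60% and 80% power requires about 0.75 SD. Report 95% confidence intervals for all three primary changes.
2. Restore the protocol 9.6.1 supplemental analysis for the three primary efficacy outcomes in the 29 tested participants. Use week 20 for completers. For early stoppers, use week 12 only if they were still on sirolimus and ART without virologic failure, and otherwise week 4. Classify them from the sirolimus stop dates that protocol 6.3.4 already requires on the CRF, and report how many contribute at each week. Present the result beside the 20-week completer test, which stays primary.
3. Optionally, add the average of treatment weeks 4, 12 and 20 for completers, as protocol 9.6.2 allows.

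The cost is a few SAP sentences and a few lines of code; no new samples need to be selected. The added estimate mixes 4, 12 and 20 weeks of exposure and may have less power than the completer test if the effect builds slowly. It does not remove selection on virologic failure, because it too is limited to time without failure. The stated power will look less favourable.
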